#### 1. PROJECT SUMMARY

Healthcare personnel (HCP) are believed to be at increased risk of influenza virus infection due to a higher rate of exposure compared with the general population. Close contact with patients may further result in transmission to patients. Vaccination is the most effective method of preventing influenza, but there is limited information on the effectiveness of influenza vaccines among HCP. Some studies have demonstrated reduced influenza vaccine immunogenicity and effectiveness among persons with a history of frequent influenza vaccination, emphasizing the need to examine influenza vaccine effects among HCP who may be frequently vaccinated or demonstrate a high baseline immune response to influenza viruses.

The primary objective of the study is to compare humoral immune responses to a single dose of recombinant hemagglutinin quadrivalent influenza vaccines (RIV4) or to standard egg-

based unadjuvanted quadrivalent influenza vaccines (IIV4) among  $HCP \ge 18$  years old who were vaccinated in the 2018-19 season with IIV4. The trial will be conducted at two hospital sites in Israel during the upcoming influenza season (2019-20) among HCP who were enrolled in the Study of Healthcare Personnel with Influenza and other Respiratory Viruses in Israel (SHIRI).

The study design is a randomized, single-blind, trial. During the study, eligible HCP at each site who consent to participate will be randomized 1:1 to receive a single dose of RIV4 (Flublok™ Quadrivalent by Sanofi, Inc., 45µg of HA per strain) versus a single dose of IIV4 (VaxigripTetra™ by Sanofi, Inc., 15µg of HA per strain). Participants will be blinded to the vaccine that they receive; study staff will not be blinded. Eligible HCP who report already having been vaccinated with Vaxigrip at the time they are approached to join the study will be eligible to participate. All randomized participants will have blood collected just prior to vaccination; all participants, including those who were vaccinated with Vaxigrip outside of the study, will have blood collected , approximately 28 days after to evaluate humoral immune responses to vaccination. Relative efficacy of single doses of study vaccines will be assessed by comparing immunologic responses to vaccination among participants receiving RIV4 and those receiving IIV4. In addition, the effect of prior vaccination in potentially modifying antibody immune responses to vaccine will be evaluated.

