# 5. STUDY ENDPOINTS

# **5.1 Primary Endpoints**

The primary endpoints will be assessed by the following laboratory tests. The choice of laboratory assay may depend in part on how the 2019-2020 vaccine components and circulating strains affect which laboratory assay is most effective in assessing specific antigens.

- HI and/or MN responses to *egg*-grown vaccine reference viruses for all vaccine viruses for each study season at approximately 28 days, including the following endpoints
  - o Seroconversion rate (SCR) defined as the proportion of participants with paired samples that achieved ≥4-fold rises comparing post- versus pre-vaccination titers
  - Geometric mean titers (GMT) and the ratio of post-vaccination titers between the two vaccines (post-vaccination GMT ratio);
  - Geometric mean-fold rise (GMR) defined as the ratio of the post-vaccination titer
     value to the pre-vaccination value
  - o Elevated post-vaccination titers at thresholds greater than 1:40, 1:80, 1:160
- MN responses to the *cell*-grown influenza A/H3N2 (using MDCK-SIAT or other appropriate cell line) vaccine reference viruses at approximately 28 days postvaccination, including the following endpoints:
  - o SCR, post-vaccination GMT ratio, GMR, and elevated post-vaccination titers

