#### 6.3.4 Randomization

Using the list of HCP consented to participate in the study, HCP will be randomized 1:1 to receive one 0.5 mL intramuscular dose of Flublok® Quadrivalent or Vaxigrip Quadrivalent. Randomization lists will be generated by the epidemiologist and data analyst using block randomization to ensure equal sample size in each group.

Randomization will be conducted after enrollment is completed. Randomization will occur separately for participants in Group One and Group Two.

Randomization will not occur for enrolled participants who were vaccinated with Vaxigrip outside of the study.

# 6.4 Study visit 1

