### 6.4.1 Pre-vaccination Questionnaire

All study participants, except those who were already vaccinated outside of the study, will complete a second brief questionnaire to determine whether they are currently experiencing fever, decreased energy, muscle aches, headache, or nausea, and will be asked to rate the subjective severity of any symptom(s) as mild, moderate, or severe (Appendix E. Prevaccination Questionnaire/Vaccine Administration Form). Appendix E will also readdress the study exclusion criteria. Participants reporting subjective fever (of any severity) and those reporting no fever but one or more symptom of moderate or severe subjective severity will not receive study vaccine until their illness has resolved. In this case, a follow up appointment will be made after resolution of the illness, at which time the participant will receive the vaccine. Study number assignment and pre-vaccination blood draw will take place on the day of vaccine administration.

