# 9.2 Statistical Analysis

HI and MN results will be measured by four primary parameters: SCR, post-vaccination GMT ratio, GMR, and post-vaccination titers equal or greater than seropositive thresholds at 1:40, 1:80, and 1:160. SCR will be defined as the proportion of participants with paired samples that achieved ≥ 4 fold rise comparing post vs pre-vaccination titers and post vaccination titers ≥ 1:40. GMR will be defined as the mean of the ratio of post-vaccination HI/MN titer and pre-vaccination HI/MN titer for each subject.

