# Primary Objective

The primary objective of the study is compare humoral antibody responses to IIV4 and RIV4 among Group One HCP as measured by HI (and MN, as appropriate) at baseline (day 0), and approximately 28 days post-vaccination. The proportion of participants that seroconverted (SCR) is defined as  $\geq$  4-fold increase comparing post- versus pre-vaccination titers. Exact 95% confidence intervals will be calculated and the SCR will be compared between vaccine groups using  $\chi^2$  or Fisher exact tests.

Due to the skewed distribution of the resulting titer values, base-2 log transformed titers will be used in analyses and then the summary statistics will be back-transformed to the original scale for presentation of results. The GMT is calculated for each vaccination group as the anti-log2(mean[log2(titeri)]), where *i* represents the titer value for each participant, and 95% confidence intervals assume a normal distribution. To allow for calculation of HI GMTs, a titer of 1:5 will be assigned to those with undetectable HI antibody.

Differences in GMT and GMR will be compared between study groups using separate linear regression models or a generalized linear model that accounted for repeated measures. Odds of achieving elevated post-vaccination titers at seropositive thresholds > 1:40, 1:80, and 1:160 will be compared between study groups by logistic regression.

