## Secondary Objectives

To compare immune responses among Group Two participants with a history of PCR-confirmed influenza infection a linear regression predicting log transformed titer will be created with independent variables for year of influenza infection, type of influenza virus detected, study arm, and potential confounders. We assume confounding will be eliminated by randomization and that models will not be adjusted unless differences in study arms are found during univariate analysis.

To assess prior vaccination status among Group One participants (number of influenza vaccinations received during the preceding 10 years) as an effect modifier of differences in GMTs, a linear regression predicting log transformed titer will be created with independent variables for vaccine history, study arm, and potential confounders, and an interaction term between study arm and vaccine history.

All primary analyses will be conducted as intention-to-treat. All tests will be 2-tailed with a level of significance of .05.

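### The primary post-vaccination GMT comparison leaves out the day-0 titre; adjusting for it would sharpen the randomised comparison at no cost beyond SAP wording

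*Combined protocol and SAP*

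**What the plan says.** Section 9.2 makes the post-vaccination GMT ratio one of four primary parameters, next to SCR, GMR and titres above fixed thresholds. Under Primary Objective it puts titres on the log2 scale and says that the GMT and GMR contrasts "will be compared between study groups using separate linear regression models or a generalized linear model that accounted for repeated measures". It names no covariate and does not say which of the two model types applies. For HI it adds that "a titer of 1:5 will be assigned to those with undetectable HI antibody".

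The only adjustment rule is in the Group Two paragraph under Secondary Objectives: "models will not be adjusted unless differences in study arms are found during univariate analysis". It gives no variable and no criterion, and the text does not say whether it reaches the primary models.

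The covariate is already collected. Section 1 states: "All randomized participants will have blood collected just prior to vaccination". Section 6.4.1 states: "Study number assignment and pre-vaccination blood draw will take place on the day of vaccine administration". Participants vaccinated outside the study are different. Section 6.1 places them in the Vaxigrip arm, and section 6.4.2 gives them an end-of-season 2018-19 sample as baseline.

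**The concern.** Pre- and post-vaccination titres in the same person are usually correlated. A day-28 comparison that ignores the day-0 titre leaves explainable variation in the error term, so its interval is wider than it need be. The GMR uses the day-0 titre, but as a change score, which is also less efficient than covariate adjustment when the correlation is below 1 and the SDs are equal.

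The repeated-measures option does not settle this. Unless the baseline means of the two arms are held equal, which the plan does not say, complete pairs give back only the raw day-28 contrast or the log change score. A rule that adjusts only after an arm difference is seen would forgo the gain in most trials. At stake are the width of the interval for a primary parameter and the power for ratios below 2.

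**Working it through.** **Inputs from the documents.** Two-sided 0.05 and 80% power; 2-fold GMT target (20 against 40, or 1 log2 unit); 5% dropout (all section 9.1). 440 in Group One (section 6.3.2). 1:1 allocation (section 6.3.4).

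**Assumed.** SD of log2 titre 1.5 to 2.5 (3 also checked), equal before and after; pre/post correlation rho 0.3, 0.5, 0.7; all 440 randomised, so n = 440/2 × 0.95 = 209 per arm.

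**The plan's own figures.** Table 2, 40% against 52%, pooled variance: n = [1.96·√(2·0.46·0.54) + 0.8416·√(0.40·0.60 + 0.52·0.48)]² / 0.12² = 269.6, so 270 per arm and 540 in total, as printed. That figure is for SCR. For the 2-fold GMT statement, unadjusted, SE = SD·√(2/209) and power = Φ(1/SE − 1.96):

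- SD 1.5: SE 0.147, power above 99.9%
- SD 2: SE 0.196, power 99.9%
- SD 2.5: SE 0.245, power 98.3%
- SD 3: SE 0.293, power 92.6%

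The GMT statement therefore holds without adjustment over this range.

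**Variance under three analyses**, relative to the raw day-28 contrast: change score 2(1 − rho); baseline-adjusted 1 − rho². Adjusted against change score is (1 + rho)/2. None of these ratios depends on n or SD.

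| rho | change/raw | adjusted/raw | adjusted/change |
|---|---|---|---|
| 0.3 | 1.40 | 0.91 | 0.65 |
| 0.5 | 1.00 | 0.75 | 0.75 |
| 0.7 | 0.60 | 0.51 | 0.85 |

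The adjusted model has the smallest variance in every row, so preferring it does not require knowing rho.

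**Smallest ratio with 80% power**, 2^(2.802·SE), with SE = SD·√((1 − rho²)·2/209):

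| SD | unadjusted | rho 0.3 | rho 0.5 | rho 0.7 |
|---|---|---|---|---|
| 1.5 | 1.33 | 1.31 | 1.28 | 1.23 |
| 2 | 1.46 | 1.44 | 1.39 | 1.31 |
| 2.5 | 1.61 | 1.57 | 1.51 | 1.40 |

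At SD 2 the 95% CI multiplier, 2^(1.96·SE), goes from 1.30 to 1.29, 1.26 and 1.21. Power at a 1.4-fold ratio, chosen only for illustration, goes from 70% to 74%, 82% and 94%.

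**Real titres are coarser.** Simulation with 209 per arm, latent SD 2, day-0 GMT 20, IIV4 day-28 GMT 40, two-fold dilutions, and values below 10 set to 5 (about 31% at the floor on day 0), at latent rho 0.3, 0.5, 0.7:

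- Variance cut against the raw contrast: about 7–9%, 23%, 42–44%, close to the formula.
- Variance cut against the change score: about 26–29%, 17%, 8%, clearly below the formula's 35%, 25%, 15%.
- Null rejection: 5.0–5.2% unadjusted and 5.1–5.4% adjusted (Monte Carlo SE 0.3 points).

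**GMT ratio and fold rise.** If log2(post) = a + τ·arm + β·log2(pre), subtracting log2(pre) from both sides gives log2(post/pre) = a + τ·arm + (β − 1)·log2(pre). The arm coefficient τ is unchanged.

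**The case against.** The strongest reply is that no stated design goal is at risk. Enrolment is sized on SCR, which this change does not touch. The only GMT target is 2-fold and is already well powered. Baseline already enters SCR and GMR. The SD and rho are assumed, and at rho 0.3 the detectable ratio moves only from 1.46 to 1.44. The separate regressions can also be read as one for GMT and one for GMR, in which case both model options return the same two contrasts. All of this stands. The open model form is missing detail, with no harm shown, and the case rests on precision alone.

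A reader might infer more, and the documents do not support it:

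- **Bias.** Among randomised participants the unadjusted contrast is unbiased. Participants vaccinated outside the study raise a separate question.
- **Inflated type I error.** Each single model holds about 5%. If the adjustment rule did reach the primary models and meant p < 0.05 on the day-0 titre (both assumed), overall error would be about 0.048, 0.043 and 0.036 at the three correlations, which is conservative. Claiming success if either the raw or the change contrast is significant would give about 9%, but the plan does not say it would do so. Those are two declared parameters, so that is a multiplicity matter.
- **An underpowered trial.** The 2-fold calculation above shows otherwise.

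Against the change score, the formula overstates the gain once dilutions and the floor are allowed for. The simulated figures are the ones to use there.

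**Conclusion.** The point holds as a free improvement in precision for the randomised Group One comparison. Against the raw day-28 contrast the variance cut is 9%, 25% or 49% at rho 0.3, 0.5 or 0.7, and nearly the same with coarse titres. Against the change score it is more realistically about 26–29%, 17% or 8%. The size depends on an SD and a correlation that the documents do not give. The detectable ratios also assume that all 440 Group One participants are randomised; fewer would raise them but leave the percentage cuts unchanged. The simulation uses the 1:5 rule, which the plan states for HI only. No size was calculated for Group Two.

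**What to change.** In section 9.2:

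1. For randomised participants with day-0 sera, name one linear model per virus and assay as the primary GMT-ratio analysis: log2(day-28 titre) = arm + log2(day-0 titre, same assay and antigen). Report the adjusted ratio with its 95% CI and keep unadjusted GMTs as descriptive.
2. State that this adjustment does not depend on any observed difference between arms.
3. Fit the groups separately, since "Randomization will occur separately for participants in Group One and Group Two". Add the same covariate to the Group Two model, which keeps year and type of infection.
4. State that the arm coefficient is the same for log2 fold rise, so the adjusted GMT-ratio and geometric fold-rise contrasts become one test.
5. State that the model applies to the randomised comparison. Participants vaccinated outside the study have no day-0 sample and need separate handling, which the plan should describe in its own place.

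The cost is SAP wording. No visit, sample or assay is added. Items 4 and 5 do have consequences: two declared parameters share one test, and the primary GMT model is confined to randomised participants. Both should be written down before the data are seen.

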## Secondary Objectives

To compare immune responses among Group Two participants with a history of PCR-confirmed influenza infection a linear regression predicting log transformed titer will be created with independent variables for year of influenza infection, type of influenza virus detected, study arm, and potential confounders. We assume confounding will be eliminated by randomization and that models will not be adjusted unless differences in study arms are found during univariate analysis.

To assess prior vaccination status among Group One participants (number of influenza vaccinations received during the preceding 10 years) as an effect modifier of differences in GMTs, a linear regression predicting log transformed titer will be created with independent variables for vaccine history, study arm, and potential confounders, and an interaction term between study arm and vaccine history.

All primary analyses will be conducted as intention-to-treat. All tests will be 2-tailed with a level of significance of .05.

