### 4. STUDY OBJECTIVES

## 4.1 Primary Objective

- Compare humoral immune responses to a single dose of RIV4 versus IIV4 at approximately 28 days after vaccination in the 2019-20 season among HCP ≥ 18 years old who were vaccinated in the 2018-19 season with IIV4 (defined as Group One) as measured by
  - hemagglutination inhibition (HI) titers for egg-grown influenza viruses A/H1N1,
     B/Yamagata, and B/Victoria, and egg-grown and cell-grown A/H3N2
  - o microneutralization (MN) titers for egg-grown and cell-grown A/H3N2 viruses

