# 4.2 Secondary Objectives

- Compare humoral immune responses to a single dose of RIV4 versus IIV4 at 28 days post-vaccination in the 2019-20 season among HCP with a history of PCR-confirmed influenza infection during any of the three study years (2016-17 through 2018-19) compared to those without PCR-confirmed influenza infection (defined as Group Two);
- Compare humoral immune responses at 28 days post-vaccination as stated in the primary objective but with secondary indicators of humoral immune response using MN titers for other virus subtypes/lineages, as appropriate;
- Examine whether the number of prior influenza vaccinations during the preceding 10 years, as documented by medical records, modifies humoral immune responses after a single dose of RIV4 or IIV4 at approximately 28 days after receipt of the 2019-20 vaccines as measured by
  - HI titers for influenza A/H1N1, influenza B/Yamagata, and influenza B/Victoria strains and
  - o MN titers for influenza A/H3N2 viruses

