### Inclusion criteria:

- 1. Aged ≥18
- 2. Are currently a member of Clalit Health Services
- 3. Consent to randomized receipt of influenza vaccination with either RIV4 or IIV4, or, if already vaccinated in the current year outside of the study, consent to receive a post-vaccination blood draw
- 4. HCP Group One participation criteria:
  - Participated in the SHIRI study and received influenza vaccination during the
     2018-19 influenza season
- 5. HCP Group Two participation criteria:
  - Participated in any year of the SHIRI study and had PCR-confirmed influenza virus infection during any of the three study years;
- 6. HCP Group One Supplemental criteria:
  - Participated in any year of the SHIRI study, not vaccinated in 2018-2019, but vaccinated in at least one study year;
  - Participated in the SHIRI study during all three years, regardless of vaccination status

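### The first secondary objective asks how HCP with and without PCR-confirmed influenza compare, but its only planned model is fitted among infected HCP, so the with-versus-without part has no planned estimate

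*Combined protocol and SAP*

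**What the plan says.** **Objective.** Section 4.2, first bullet, compares RIV4 with IIV4 responses at 28 days in HCP with PCR-confirmed influenza in any of the three SHIRI seasons, "compared to those without PCR-confirmed influenza infection (defined as Group Two"). The third bullet of the same section, on vaccination history, uses different language: it asks whether the number of prior vaccinations "modifies humoral immune responses after a single dose of RIV4 or IIV4".

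**Groups.** Section 6.3.1 admits to Group Two only HCP who took part in any SHIRI year and "had PCR-confirmed influenza virus infection during any of the three study years". Group One is defined by vaccination: "Participated in the SHIRI study and received influenza vaccination during the" 2018-19 season. Section 4.1 describes it in the same way: HCP "who were vaccinated in the 2018-19 season with IIV4 (defined as Group One"). Neither definition excludes prior infection. Group One Supplemental can add HCP who "Participated in any year of the SHIRI study, not vaccinated in 2018-2019, but vaccinated in at least one study year".

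**Analysis.** Section 9.2 gives one model for the first secondary objective: a linear regression of log titre among Group Two participants with a history of PCR-confirmed infection, with "independent variables for year of influenza infection, type of influenza virus detected, study arm, and potential confounders". The next paragraph, on vaccination history in Group One, does specify an arm-by-history interaction. The primary analysis is to "compare humoral antibody responses to IIV4 and RIV4 among Group One HCP".

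**The concern.** The objective names two populations and the model contains one. An analyst who follows section 9.2 exactly will report an arm contrast within infected HCP and differences by year and virus type, but nothing that sets infected against uninfected.

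The estimand is also open. The bullet could mean the arm effect within infected HCP, the response of infected versus uninfected HCP, or a change in the arm effect with infection history. The last is the most natural reading, but the text says compare rather than modify.

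The label adds to this. In section 4.2 the Group Two definition follows the uninfected clause, while section 6.3.1 makes Group Two the infected group.

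At stake is one part of one secondary objective. If the gap stays, the comparator, the estimand and the adjustment could all be settled after titres are known.

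**Working it through.** **1. The plan's own figure.** The plan gives no sample size or power for this comparison. Table 2 sizes the arm contrast. Its row for SCR 40% with a 30% relative increase reproduces: [1.960 x sqrt(2 x 0.46 x 0.54) + 0.842 x sqrt(0.40 x 0.60 + 0.52 x 0.48)]^2 / 0.12^2 = 269.6, so 270 per arm and 540 in total. It does not bear on the point.

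**2. What the planned model can estimate.**
- Population: infected Group Two only, so there is no uninfected row in the data.
- Year of infection and virus type have no value for an uninfected person. Coding them as none would not help, because the population is restricted.
- Arm coefficient: RIV4 versus IIV4 within infected HCP.
- Infected versus uninfected, as a main effect or as a modifier of arm: no coefficient.
- No other section supplies one. The primary analysis covers arm contrasts in Group One only.

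**3. Why Group One is not a clean uninfected comparator.** It does not exclude prior infection. Its core members were all vaccinated in 2018-19, which Group Two does not require. Suppose a reader nevertheless sets the two groups' arm contrasts side by side. Assume no true infection effect, an RIV4/IIV4 GMT ratio of 2 in 2018-19 vaccinees and 1 in others, a share p of Group Two vaccinated in 2018-19, and a share g of Group One. The apparent ratio of ratios is 2^(p - g).

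| p | g = 1.0 | g = 0.9 (10% unvaccinated) |
|---|---|---|
| 0.5 | 0.71 | 0.76 |
| 0.7 | 0.81 | 0.87 |
| 0.9 | 0.93 | 1.00 |

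If vaccination does not modify the arm effect, every entry is 1.0. The 2-versus-1 modification and the shares are assumptions.

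**4. Which vaccination term the fix needs.** With g = 1 and p = 0.5, 2018-19 vaccination as a main effect only still returns 0.71, because it leaves the arm effect the same in vaccinated and unvaccinated HCP. Adding arm x 2018-19 vaccination returns 1.0.

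The 10-year count does not do this job. Suppose the other nine seasons are independent, each with probability 0.5 (variance 9 x 0.25 = 2.25), and 104 of 522 participants are infected:
- pooled within-group covariance of 2018-19 status with the count = (104/522) x 0.25 = 0.050
- slope = 0.050 / (0.050 + 2.25) = 0.022
- residual bias = -0.5 + 0.022 x 0.5 = -0.489 log2, which is 0.71 fold

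Simulations with other assumed count distributions, including counts correlated with 2018-19 status, gave values up to 0.77.

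**5. Precision of the missing estimate.** Inputs: 440 Group One and 110 Group Two (section 6.3.2), 5% drop-out (section 9.1), 1:1 arms (section 6.3.4), two-sided 0.05 and 80% power, so z = 1.960 + 0.842 = 2.802. This gives 110 x 0.95 = 104 infected and 440 x 0.95 = 418 treated as uninfected. The documents give no SD, so log2 SDs of 1.0, 1.5 and 2.0 are assumed. No gain from baseline adjustment is counted.

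Without vaccination terms, SE = 2 x SD x sqrt(1/104 + 1/418) = 0.219 x SD. With arm x vaccination and all uninfected vaccinated, the contrast rests on the vaccinated infected only, so SE = 2 x SD x sqrt(1/(104p) + 1/418). The detectable ratio of GMT ratios is 2^(2.802 x SE).

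| Model | SE / SD | SD 1.0 | SD 1.5 | SD 2.0 |
|---|---|---|---|---|
| No vaccination terms | 0.219 | 1.53 | 1.89 | 2.34 |
| arm x vaccination, p = 0.9 | 0.229 | 1.56 | 1.95 | 2.43 |
| arm x vaccination, p = 0.7 | 0.254 | 1.64 | 2.10 | 2.68 |
| arm x vaccination, p = 0.5 | 0.294 | 1.77 | 2.36 | 3.13 |

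These are illustrations, not bounds. If 10% or 20% of Group One were in fact infected and moved to the infected stratum, the split would be about 146/376 or 188/334, and the SE without vaccination terms would fall to 0.195 or 0.182 x SD. HCP vaccinated outside the study are not randomised (section 6.3.4), and removing them works the other way.

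**The case against.** **The objective may mean only the arm effect within infected HCP, with the Group Two label attached to the whole bullet.** That is possible, and the planned model would then suffice. But the clause about those without infection would have no function and the bullet would need rewording. The estimand has to be stated either way.

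**Group One can serve as the comparator.** No comparison between the groups is planned, and Group One differs from Group Two in required 2018-19 vaccination as well as in infection history. Section 9.2 assumes that randomisation removes confounding. That covers arm contrasts, but infection history is not randomised.

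**The bias figures describe an analysis that nobody plans.** This stands. They rest on an assumed modification and shrink to 0.76, 0.87 and 1.00 if 10% of Group One were unvaccinated in 2018-19. They show why the added model needs a vaccination interaction and do not measure error in a planned result.

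**The scope is small and the steering committee confirms analysis plans (section 11.1).** The scope is indeed limited. The committee's role makes the correction easy, but it does not supply the missing analysis.

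A reader might infer that the whole first secondary objective lacks an analysis, or that the primary result is compromised. The documents support neither: the arm contrast within infected HCP is planned, and the primary objective is analysed in Group One without reference to infection history.

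**Conclusion.** The mismatch is real and follows from the text alone. Followed as written, the plan gives no estimate or test for the with-versus-without part of its first secondary objective, and section 4.2 contradicts section 6.3.1 on who Group Two is. It should be corrected, as a defect in one secondary objective.

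No size can be put on an estimate that is not planned. What can be said is that the added interaction will be imprecise. Under the assumed SDs and vaccinated shares, only ratios of GMT ratios of about 1.5 to 3.1 fold would be detectable at 80% power. It would be too strong to say that the objective must be about effect modification: that is the most natural reading, but the documents do not state it.

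**What to change.** 1. In section 4.2, correct the Group Two label and state the estimand. The most natural choice is the ratio of RIV4/IIV4 GMT ratios, infected versus uninfected, with the GMT ratio also reported in each stratum.
2. In section 9.2, add one model in all randomised participants: log2(post titre) on arm, PCR-confirmed infection (from linked SHIRI data, not recruitment group), arm x infection, 2018-19 vaccination (yes/no), arm x 2018-19 vaccination, and log2(pre titre). Report arm x infection with its 95% CI. The 10-year count should not replace the 2018-19 indicator.
3. Define uninfected as no PCR-positive result in observed SHIRI seasons. A sensitivity analysis in HCP followed for all three seasons is optional, because PCR status in unobserved seasons cannot be recovered.
4. Keep the year and virus-type model within infected HCP.

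**Cost.** Wording in two sections and one coding rule for unobserved seasons. Section 6.7 already provides for linking SHIRI data and extracting vaccination history, so no new visits, samples or participants are needed. The downside is imprecision, and the plan should say that a non-significant interaction must not be read as no difference.
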